3.0 Study Design and Eligibility Criteria

3.1 Study Design (see also Study Schema, page 3)

- 3.1.1 We propose a Phase II single-arm trial of azacitidine (IV or SC) in combination with escalating donor lymphocyte infusions (DLI). This study will be open to patients with ALL, AML, JMML, or MDS.
- 3.1.2 The first cycle of azacitidine will be administered during withdrawal of immunosuppression for patients not developing severe organ toxicity or Grade III-IV GVHD.
- 3.1.3 After the initial cycle during withdrawal of immunosuppression (duration is based on day 28 PB chimerism), azacitidine is given for 4 days in 6-week cycles (+/- 2 weeks) at a dose of 40 mg/m²/day.
- 3.1.4 For patients meeting High Risk criteria who have available cell product, DLI is given on day 5 of each cycle in escalating doses. Peripheral blood chimerism and MRD is assessed after week 4, prior to initiating the next cycle. BM chimerism and MRD is

obtained at regular intervals prior to specified cycles as per the study schedule. Patients will receive up to 7 cycles as tolerated.

3.1.5 Patients will be followed by laboratory monitoring and physician evaluation prior to each cycle. Weekly labs will be obtained and will include toxicity monitoring (CBC, LFTs, and electrolytes) and correlative studies, such as immunophenotype and T cell function by PHA. Patients will be followed for two years to study toxicity and GVHD outcomes as well as relapse incidence.

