5.3 Risk Stratification

- 5.3.1 Risk is evaluated and assigned prior to each azacitidine cycle based on clinical testing specific to that patient's disease.
- 5.3.2 For patients with MDS, any evidence of disease may be used to stratify the patient accordingly. In the absence of evidence of persistent disease, chimerism will be used to stratify the patient. MDS patients with no evidence of disease and 100% chimerism will be stratified as standard risk.
- 5.3.3 Peripheral blood disease assessment will be done as clinically indicated. Peripheral blood MRD by deep sequencing (if positive) may be used to risk-stratify ALL patients instead of bone marrow MRD. Any evidence of disease in peripheral blood for patients with AML/JMML or MDS will prompt BM evaluation as clinically indicated. In this instance, study treatment may continue after BM evaluation is complete.
- 5.3.4 Risk stratification criteria:
 - Low Risk
 - May only be applied to acute lymphoblastic leukemia patients
 - All of the following
 - Pre-transplant deep sequencing MRD negative, AND
 - All post-transplant deep sequencing MRD samples negative, AND
 - Any chimerism or GVHD status
 - ALL patients with negative deep-sequencing MRD pre- and post-transplant will be treated as low-risk regardless of chimerism
 - Standard Risk
 - Active Grade I GVHD, OR
 - Any history of Grade II (or higher) GVHD, OR
 - All of the following
 - Full Donor Chimerism AND
 - Pre-HSCT MRD $<10^{-5}$ (bone marrow) AND
 - Post-HSCT MRD $<10^{-5}$ (bone marrow), unless 3-fold increase is observed
 - High Risk
 - No active acute or chronic GVHD, AND
 - No history of Grade II (or higher) acute GVHD or chronic GVHD, AND

- Any of the following:
 - Mixed chimerism OR
 - Pre-HSCT MRD $> 1 \times 10^{-5}$ OR
 - Post-HSCT MRD at day 28 or later $\geq 10^{-5}$ once, OR
 - Post-HSCT MRD at day 28 or later $\geq 10^{-6}$ with ≥ 3 -fold increase on any subsequent measurement (need not be consecutive).
 - Post-HSCT MRD $< 1 \times 10^{-5}$ is treated as Standard Risk until a 3-fold increase is documented.

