- Azacitidine without DLI: Patients meeting Standard Risk criteria will receive azacitidine without DLI at a dose of 40mg/m² IV or SC x 4 days every 6 weeks. DLI should be considered for patients with resolved Grade 2 GHVD if pre- or post-transplant MRD is positive.
- Azacitidine with DLI: Patients meeting High Risk criteria, who also have available cells, will receive DLI in addition to azacitidine. Patients with history of Grade 2 GVHD (which has resolved) may also receive DLI if pre- or post-transplant MRD is positive at the discretion of the treating physician.
 - Administration of azacitidine following withdrawal of immunosuppression will commence (typically on a Monday) 2-8 weeks following *completion* of SWI/FWI (see section 6.2 for dose adjustments).
 - Azacitidine will be given at a dose of 40mg /m² IV or SC daily for 4 days every 6 weeks.
 - Escalating doses of DLI will be administered (typically on a Friday) within 5 days following the last dose of azacitidine every cycle (see section 5.8 for DLI schedule).
 - For patients with negative pre- and post-transplant MRD:
 - Once MDC resolves to FDC in both blood and bone marrow, DLI will be discontinued and patient will continue to receive azacitidine alone for a maximum of 7 cycles as tolerated.
 - If FDC is detected in blood, bone marrow chimerism must be obtained and confirmed to be mixed before proceeding with DLI.
- If DLI is administered without azacitidine during cycles 2 through 7, the subject should continue with all subsequent study assessments, but will be analyzed separately with regard to safety and efficacy.
- Cycles may be delayed for reasons such as toxicity, as per dose adjustment section 6.0.
- For all patients who receive azacitidine, a total of 7 cycles may be administered as tolerated.

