5.8.3 Pre-Transplant MRD positive

- Patients with pre-transplant MRD $>10^{-5}$ are eligible to receive escalating DLI regardless of chimerism status if there is no active GVHD.
- If no active GVHD, DLI should continue until maximum DLI dose is achieved.

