5.8.4 Post-Transplant MRD positive

- For patients with persistent MRD post-transplant ($>1 \times 10^{-5}$ or 1×10^{-6} and increasing) and with no active GVHD, azacitidine and escalating doses of DLI should be administered.
- DLI should be escalated to maximum dose and administered while MRD remains positive. If MRD is positive after cycle 7, DLI may be administered with or without azacitidine after discussion with the study chair.

5.9 Intra-patient DLI dose escalation to be used on day 5 (following 4 days of azacitidine):

5.9.1 Mismatched related donor or any unrelated donor:

- 1st dose: 5×10^5 /kg -- 1×10^6 /kg of CD3+ cells
- 2nd dose: 1×10^6 /kg -- 1×10^7 /kg of CD3+ cells
- 3rd and all subsequent doses: 1×10^7 /kg -- 5×10^7 /kg of CD3+ cells

5.9.2 Matched related donor:

- 1st dose: 1×10^7 /kg of CD3+ cells
- 2nd and subsequent doses: 5×10^7 /kg of CD3+ cells

5.9.3 Peripheral blood chimerism will be repeated during or after week 4 of every cycle, and the next cycle will not be initiated until results are obtained.

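### For children MRD-positive before transplant but MRD-negative and fully donor-chimeric after it, 5.8.3 reads as ending DLI at a maximum dose while 3.1.4 gives DLI every cycle, and that maximum is undefined for mismatched or unrelated donors

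*Combined protocol and SAP*

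**What the plan says.** - **5.8.3 (pre-transplant MRD positive).** These patients may receive escalating DLI whatever their chimerism, provided GVHD is not active. Then: "If no active GVHD, DLI should continue until maximum DLI dose is achieved".
- **5.8.4 (post-transplant MRD positive).** A differently worded rule: "DLI should be escalated to maximum dose and administered while MRD remains positive".
- **3.1.4 (study design).** For High Risk patients with cell product available, "DLI is given on day 5 of each cycle in escalating doses". It names no exception and does not point to 5.8.
- **5.3.1 and 5.3.4 (risk).** "Risk is evaluated and assigned prior to each azacitidine cycle". Without active GVHD or a disqualifying GVHD history, pre-transplant MRD above 1x10^-5 is enough for High Risk.
- **5.7.6 (azacitidine with DLI).** "Patients meeting High Risk criteria, who also have available cells, will receive DLI in addition to azacitidine". The instruction to drop DLI once blood and marrow are fully donor is limited to patients MRD-negative both before and after transplant.
- **5.9 (dose steps, CD3+/kg).** Mismatched related or any unrelated donor: first dose 5x10^5 to 1x10^6, second 1x10^6 to 1x10^7, and "3rd and all subsequent doses" 1x10^7 to 5x10^7. Matched related donor: first dose 1x10^7, then 5x10^7 for the second and later doses.

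No section defines the maximum DLI dose or says which section prevails.

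**The concern.** Consider a child who was MRD-positive before transplant and afterwards is MRD-negative, fully donor-chimeric and free of GVHD. Section 5.8.3, read plainly, sets an end point for DLI. The wording of 5.8.4 supports that reading, because there the authors expressly provided for dosing beyond the maximum while MRD persists. Section 3.1.4 gives the same child DLI in every cycle. Two sites could each follow the protocol and give different numbers of infusions.

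Section 9.1 puts the risk of GVHD after withdrawal of immunosuppression and DLI at 50 to 65%, with about a 10% chance of dying from it. Section 8.7.3 reviews grade III-IV acute GVHD and GVHD mortality in DLI recipients as one group and can suspend enrolment on the result. If sites apply different stop rules, that group mixes different planned exposures for a reason unrelated to the patients.

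**Working it through.** **Which rules reach this child**

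1. Pre-transplant MRD is a fixed baseline fact. Under 5.3.4 the child is High Risk at each pre-cycle assessment unless GVHD occurs.
2. High Risk with cells available means DLI each cycle under 3.1.4.
3. The chimerism stop in 5.7.6 does not apply, because the child was MRD-positive before transplant.
4. 5.8.2 (mixed chimerism) and 5.8.4 (post-transplant MRD) do not apply, so neither supplies a separate reason to go on. Only 5.8.3 and 3.1.4 remain, and they differ.

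**How far the readings differ**

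The plan states no number of DLIs and no cumulative dose, so there is no figure to reproduce. Table 1 gives cycle 1 as azacitidine alone, and the text under Figures 1a and 1b allows up to 6 further courses. DLI is therefore possible in cycles 2 to 7, at most k = 6 times. The doses below come from 5.9. Stopping means giving no more DLI after the first dose at the top step.

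- **Matched related.** Stop: 1x10^7 + 5x10^7 = 6x10^7 (2 DLIs). Every cycle: 1x10^7 + (k-1) x 5x10^7; k = 6 gives 2.6x10^8.
- **Mismatched or unrelated, low end of each range.** Stop: 5x10^5 + 1x10^6 + 1x10^7 = 1.15x10^7 (3 DLIs). Every cycle: 1.5x10^6 + (k-2) x 1x10^7; k = 6 gives 4.15x10^7.
- **Mismatched or unrelated, high end of each range.** Stop: 1x10^6 + 1x10^7 + 5x10^7 = 6.1x10^7 (3 DLIs). Every cycle: 1.1x10^7 + (k-2) x 5x10^7; k = 6 gives 2.11x10^8.

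Ratio of every-cycle to stop-at-maximum cumulative dose:

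| DLIs delivered (k) | Matched related | Mismatched/unrelated, low | Mismatched/unrelated, high |
|---|---|---|---|
| 6 | 4.3 | 3.6 | 3.5 |
| 5 | 3.5 | 2.7 | 2.6 |
| 4 | 2.7 | 1.9 | 1.8 |
| 3 | 1.8 | 1.0 | 1.0 |

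**What the undefined maximum adds**

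The low-end column counts arrival at the third step as the maximum. If the maximum is instead 5x10^7/kg, a child held at the permitted 1x10^7/kg never reaches it. DLI then continues under 5.8.3 as well. For that child the meaning of the term decides between 3 and 6 infusions. For matched related donors the question does not arise, since 5.9.2 gives a single top value, reached at the second DLI.

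**The case against.** The strongest reply is that 5.8.3 is a specific rule qualifying a general one. The last bullet of 5.8.2 says that full donor chimeras ordinarily get no more DLI, apart from the exceptions that follow. 5.8.3 can be read as one of those exceptions, with its own end point. The timing sentence in 5.7.6 also defers to it: "following the last dose of azacitidine every cycle (see section 5.8 for DLI schedule". Section 5.9 sets amounts, not frequency, and its later doses are needed anyway for patients under 5.8.2 and 5.8.4. A different rule in 5.8.4 for a different population is not itself a conflict. Much of this stands. A reader might infer that 5.8.3 also contradicts 5.7.6 and 5.9, but the direct conflict is with 3.1.4 alone. It remains because 3.1.4 is unqualified and no text ranks the sections.

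Three other stronger readings are not supported:

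- **Overlapping dose ranges.** The 5.9.1 ranges meet only at 1x10^6 and 1x10^7 and are indexed by dose number, so a child's step is always known.
- **A maximum undefined for everyone.** It is fixed for matched related donors.
- **An 18-fold difference** (2.11x10^8 / 1.15x10^7 = 18.3). This combines the stop-rule question with the width of the 5.9.1 ranges. The width alone gives about five-fold (6.1x10^7 / 1.15x10^7 = 5.3; 2.11x10^8 / 4.15x10^7 = 5.1), and it applies to any mismatched or unrelated DLI recipient whatever 5.8.3 means.

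It is also fair that exposure varies by design. DLI depends on risk, GVHD and available product, and 6.1 allows case-by-case dose changes. Section 8.6.2 plans simple proportions with no dose-exposure analysis, and section 15 already requires records of quantity given. These points limit the consequence but do not supply the missing stop rule.

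**Conclusion.** The point holds for a defined group: pre-transplant MRD-positive children who after transplant are MRD-negative, fully donor-chimeric and without GVHD. For them 5.8.3 and 3.1.4 support different numbers of DLIs. For mismatched or unrelated donors the trigger in 5.8.3 cannot be applied uniformly, because its maximum is undefined.

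The stop rule alone changes cumulative CD3+ dose 3.5- to 4.3-fold. That assumes all six DLIs are delivered, with enough cells and no GVHD, and that for mismatched or unrelated donors the third step counts as the maximum. Fewer DLIs shrink the ratio, to no difference at three for those donors.

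The documents do not give the size of this group or a relation between cumulative cell dose and GVHD or relapse. A reader might infer a particular distortion of the GVHD or relapse rate, but none can be calculated. What is shown is an ambiguity in planned exposure, in a component whose safety the protocol monitors closely.

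**What to change.** Reconcile 5.8.3 with 3.1.4, and align the cross-reference in 5.7.6, so that one DLI stop rule applies to this group. State what maximum DLI dose means under 5.9.1: reaching the third step, or reaching a stated CD3+ dose. The dose steps need not change for this purpose. The sponsor's clinical team chooses the rule and the doses.

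The cost is a wording amendment. The small downside is less latitude for sites.

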5.8.4 Post-Transplant MRD positive

- For patients with persistent MRD post-transplant ($>1 \times 10^{-5}$ or 1×10^{-6} and increasing) and with no active GVHD, azacitidine and escalating doses of DLI should be administered.
- DLI should be escalated to maximum dose and administered while MRD remains positive. If MRD is positive after cycle 7, DLI may be administered with or without azacitidine after discussion with the study chair.

5.9 Intra-patient DLI dose escalation to be used on day 5 (following 4 days of azacitidine):

5.9.1 Mismatched related donor or any unrelated donor:

- 1st dose: 5×10^5 /kg -- 1×10^6 /kg of CD3+ cells
- 2nd dose: 1×10^6 /kg -- 1×10^7 /kg of CD3+ cells
- 3rd and all subsequent doses: 1×10^7 /kg -- 5×10^7 /kg of CD3+ cells

5.9.2 Matched related donor:

- 1st dose: 1×10^7 /kg of CD3+ cells
- 2nd and subsequent doses: 5×10^7 /kg of CD3+ cells

5.9.3 Peripheral blood chimerism will be repeated during or after week 4 of every cycle, and the next cycle will not be initiated until results are obtained.

5.10 Schedule of safety parameter studies

5.10.1 Pre-therapy laboratory evaluations should be completed within 7 days prior to each azacitidine cycle:

- Liver function (AST, ALT, bilirubin) and renal function (creatinine) tests
- Complete blood count (consider bone marrow aspiration if cytopenias develop if clinically indicated).
- T cell number / function: Lymphocyte phenotyping, quantitative regulatory T cells, T cell function (PHA)
- Chimerism testing as noted above.

- MRD (BM) by flow cytometry. Peripheral blood MRD (flow, DSMRD for ALL) may be sent at the discretion of the treating physician.

5.10.2 Pre-therapy clinic visit should be conducted within 14 days prior to the cycle start date.

5.10.3 On-therapy evaluations:

- Weekly liver function and renal function tests while receiving azacitidine. If patients have tolerated two cycles of azacitidine without requirement for further intervention, complete blood count, liver and renal function tests may be performed every two weeks during their remaining cycles.
- Bone marrow aspiration for MRD and chimerism as above every 2 cycles (or with each cycle if PB chimerism is 100% and BM chimerism remains mixed).

5.11 Schedule of correlative studies

5.11.1 T cell number and function with each cycle will be assessed while receiving azacitidine.

5.11.2 AML gene expression and mutation panel (AML-GEMP) will be assessed in those patients with a diagnosis of AML. Samples from BM and PB will be collected at day +30, +90 and +180 (+/- 14 days) (see Appendix 4).

Evaluation	Prior to enrollment	Prior to FWI/ SWI/ Day 28 (can be between Day 21 and Day 42)	Prior to each azacitidine cycle	Weekly during azacitidine	3 and 6 months post HCT (+/- 28 days) ³	From 9 months to 24 months post- HCT: Every 3 months (+/- 28 days) ³
History and Physical (including GVHD assessment)	X	X	X		X	X
Routine labs ¹	X	X	X	X ¹	X	X
Peripheral Blood: Chimerism and Minimal Residual Disease		X	X			
Bone Marrow: Chimerism and minimal residual disease		X ²	X ²		X ²	X ²
T cell number / function		X	X ³			
Peripheral Blood: AML gene expression and mutation panel (AML-GEMP) Optional		X			X	
Bone marrow: AML-GEMP Optional		X			X	

Table 2: Schedule of required investigations

1. Routine labs to include Complete Blood Count with differential, and chemistry including serum creatinine, AST, ALT, bicarbonate and total bilirubin within 1 week prior to azacitidine administration. If a patient has tolerated two cycles of azacitidine without requirement for

further intervention, complete blood count, liver and renal function tests may be performed every two weeks during their remaining cycles.

2. BM aspiration should be performed every other cycle (including day +30 and day +90). However, if patient is found to be FDC on peripheral blood sample, the next cycle that includes DLI cannot be initiated until BM chimerism is obtained and mixed BM chimerism is confirmed (unless DLI is indicated for (+) MRD). The following will be investigated with each BM exam (not including correlative samples): Chimerism, morphology, MRD (by flow cytometry, and/or FISH, PCR, and/or deep sequencing (DS-MRD). Whenever possible, the most sensitive MRD technique should be used. Correlative AML-GEMP will be collected and sent to the NIH on days +30, +90, and +180.
3. If a 3-monthly time point coincides with a pre-cycle assessment, a separate 3-monthly assessment does not need to be completed. However, bone marrow MRD/chimerism and AML-GEMP specimens, if applicable, must be included with the pre-cycle assessments. If azacitidine cycles have been deferred, patients should undergo the required assessments including chimerism and lymphocyte quantification and function at least every 3 months.

5.12 Duration of study participation and follow-up

All patients will be followed as part of routine clinical care at a frequency of no less than every 3 months for at least 2 years post-transplant. All patients will have a thorough history and physical exam as well as laboratory monitoring for signs of GVHD as part of routine clinical care for the duration of the study (2 years post-transplant).

6.0 Toxicity Management and Dose Modifications

6.1 DLI Toxicity: GVHD

- DLI will be GCSF-mobilized unless otherwise specified; DLI dose modifications may be made on a case-by-case basis. See Appendix 3 for additional details regarding toxicity management.
- As soon as GVHD is suspected, all further DLI or withdrawal of immunosuppression should be stopped and the patient monitored, regardless of chimerism or MRD status.
- Azacitidine may continue at the discretion of the treating physician for grade I-II acute GVHD (aGVHD) or mild chronic GVHD (cGVHD).
- If aGVHD or cGVHD is confirmed, the patient should initiate therapy as per institutional standard of care.
- All instances of aGVHD or cGVHD in patients in the intervention group should be reported to the study chair within 10 days of learning about them, and grade III-IV aGVHD and severe cGVHD should be reported within 24 hours of learning about them (see Adverse Events Section 11.0).
- At each instance of grade III-IV aGVHD or cGVHD reported in the study, subgroup analysis will be performed in the high-risk group in order to monitor safety of DLI, as outlined in section 8.7.

6.2 Azacitidine Toxicity

Guidelines for adjusting azacitidine dose administration are based on the Common Terminology Criteria for Adverse Events (CTCAE version 4.0) applied to patient reports, history and physical, and laboratory evaluations performed each cycle. Laboratory evaluations for toxicity will be performed the week prior to each cycle. Dose adjustments are as follows (28):

- 6.2.1 Development of drug-related grade 4 organ toxicity or severe infection:
 - Discontinuation of azacitidine

- 6.2.2 Hematologic toxicity:
 - Grade I-II toxicity: No dose adjustment is required.

- For platelets <30,000/uL on a stable transfusion regimen, 50% dose reduction is recommended.
- For platelets <15,000/uL, hold therapy until toxicity improves.
- For neutrophils <750 not responsive to GCSF, 50% dose reduction is recommended.
- For neutrophils <500 not responsive to GCSF, hold therapy until toxicity improves.
- See Appendix 5 for guidelines on subsequent dose adjustments based on nadir counts.

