5.7 Schedule of azacitidine administration

Azacitidine may be held or dose-adjusted based on the parameters below. If azacitidine is held > 6 weeks, the patient will remain on study but will be included in a separate analysis with regard to safety and efficacy.

5.7.1 Cytopenias prior to Cycle 1 require dose reductions as outlined below. Cytopenias following subsequent cycles require dose adjustments based on nadir counts as outlined in appendix 5.

- For platelets $< 30,000/\mu\text{L}$, 50% dose reduction is recommended.
- If platelet transfusion dependent, hold therapy until platelets $> 30,000/\mu\text{L}$.
- For neutrophils < 750 not responsive to GCSF, 50% dose reduction is recommended.
- For neutrophils < 500 not responsive to GCSF, hold therapy until toxicity improves.

5.7.2 Renal insufficiency:

- Creatinine $< 2X$ baseline: No dose adjustment is required.
- Creatinine 2-3X above baseline: Hold therapy until AKI resolves. Restart therapy at 50% dose reduction. If well-tolerated, full dose may be administered.

5.7.3 Hepatotoxicity:

- AST/ALT <5x ULN: No dose adjustment is required.
- AST/ALT 5-20x ULN: Hold therapy until transaminitis resolves. May consider 50% dose reduction and close monitoring.
- AST/ALT >20x ULN: Hold therapy until transaminitis resolves
- Total bilirubin 3-10x ULN: Hold therapy until resolution; may consider 50% dose reduction and close monitoring
- Total bilirubin >10x ULN: Hold therapy until resolution.

5.7.4 For other toxicities, repeat test twice weekly:

- Other laboratory abnormalities to be evaluated on a per-patient basis. Options include holding azacitidine until resolution, versus starting azacitidine at 50% dose reduction at the PI and treating physician's discretion.

5.7.5 Except for ALL patients classified as Low Risk, administration of azacitidine will commence during SWI or FWI if criteria are met (see section 6.2 for dose adjustment guidelines).

- Azacitidine will be given at a dose of 40mg /m² IV or SC daily for 4 days

5.7.6 Administration of azacitidine following SWI or FWI:

- PB and BM chimerism and MRD will be obtained as above and risk will be reassessed.
- No Intervention: For Low Risk ALL patients, azacitidine will be deferred. Patients will receive standard treatment and will be followed by BM every 3 months for 9-12 months.

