19.5 Appendix 5: Azacitidine dose adjustments

A) Decrease in Serum Bicarbonate

1. Unexplained reductions of serum bicarbonate to less than 20 mEq/L occurring during therapy: decrease dose by 50% on the next treatment course

B) Myelosuppression

1. For patients with baseline WBC of $3 \times 10^9/L$ or greater, absolute neutrophil count (ANC) of $1.5 \times 10^9/L$ or greater, and platelets of $75 \times 10^9/L$ or greater, adjust dose using nadir counts for any given cycle as follows:

Nadir Counts		% Dose in the Next Course
ANC ($\times 10^9/L$)	Platelets ($\times 10^9/L$)	
less than 0.5	less than 25	50%
0.5 to 1.5	25 to 50	67%
greater than 1.5	greater than 50	100%

2. For patients with baseline WBC less than $3 \times 10^9/L$, absolute neutrophil count (ANC) less than $1.5 \times 10^9/L$, or platelets less than $75 \times 10^9/L$, adjust dose based on nadir counts and bone marrow biopsy cellularity at time of nadir as shown in the table below, **unless there is a clear improvement with differentiation at the time of the next cycle, in which case the dose of the current treatment should be continued** :

WBC or Platelet Nadir % Decrease in Counts from Baseline ↓	Bone Marrow Biopsy Cellularity at Nadir		
	30 to 60	15 to 30	less than 15
	% Dose in the Next Course		
50 to 75	100%	50%	33%
more than 75	75%	50%	33%

3. If a nadir as defined in the table has occurred and both the WBC and platelet counts are more than 25% above the nadir and rising, the next course should be given at least 28 days after the start of the preceding course. If the WBC and platelet counts are not at least 25% above the nadir by day 28, counts should be reassessed every 7 days. If a 25% increase has not occurred by day 42, the patient should be treated with 50% of the scheduled dose.

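### At day 42 of a later azacitidine cycle, section 6.2.2 holds a child with platelets below 15,000/uL, Appendix 5 B.3 treats the same child at 50%, and neither is said to govern

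*Combined protocol and SAP*

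**What the plan says.** Section 6.2 of the protocol applies before every cycle: "Laboratory evaluations for toxicity will be performed the week prior to each cycle". Within it, 6.2.2 gives two holds on absolute counts. For platelets: "For platelets <15,000/uL, hold therapy until toxicity improves". For neutrophils: "For neutrophils <500 not responsive to GCSF, hold therapy until toxicity improves". The list ends with a pointer: "See Appendix 5 for guidelines on subsequent dose adjustments based on nadir counts".

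Appendix 5 B has three parts. B.1 is a nadir table for children with adequate baseline counts ("adjust dose using nadir counts for any given cycle as follows"). B.2 is a table for children with low baseline counts, based on the percentage fall in WBC or platelets and on marrow cellularity. B.3 governs when the next course is given after a nadir defined in the table. It allows re-treatment from day 28 if both WBC and platelets are more than 25% above the nadir and rising. Otherwise: "If the WBC and platelet counts are not at least 25% above the nadir by day 28, counts should be reassessed every 7 days". It closes with: "If a 25% increase has not occurred by day 42, the patient should be treated with 50% of the scheduled dose". B.3 contains no minimum platelet or neutrophil count.

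The cross-references point both ways. Section 5.7.1, repeated in Appendix 4, says: "Cytopenias following subsequent cycles require dose adjustments based on nadir counts as outlined in appendix 5". Section 5.7.6 refers dosing after the immunosuppression taper to section 6.2, and delays for toxicity to section 6.0. Appendix 4 also refers to section 6.2, but only for Cycle 2.

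**The concern.** The two rules measure recovery differently. Section 6.2.2 asks whether the current count is above a fixed floor. B.3 asks whether the count has risen by a quarter from its own nadir, and a child who fails that test at day 42 is to be treated at half dose. A child with very low, flat platelets fails both tests and receives opposite instructions.

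Day 42 is the nominal start of the next cycle under the 6-week schedule in 3.1.3. A site working from Appendix 5 would give a myelosuppressive drug to a child whom 6.2.2 tells it to hold. Section 9.2 names bleeding and infection from hematologic toxicity as the main azacitidine risks. With three institutions enrolling, the action should not depend on which page a site opens.

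**Working it through.** There is no planned figure to reproduce. The check compares the two rules as conditions on the same child.

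**Inputs**
- Hold limit: platelets below 15,000/uL (6.2.2).
- Day-42 rule: qualifying nadir, no 25% rise, treat at 50% (Appendix 5 B.3).
- Course: 40 mg/m2/day for 4 days; 6-week cycles, plus or minus 2 weeks (3.1.3).
- Already-reduced doses: 75%, 67%, 50% or 33% (Appendix 5 B.1 and B.2).

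I read B.3 as triggered when either WBC or platelets fall short, because its early re-treatment sentence requires both to have risen. If both had to fall short, fewer children would be affected, but the platelet boundary below would not move.

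**Where both rules apply.** Let N be the platelet nadir and P the day-42 count. Section 6.2.2 holds if P < 15,000. B.3, triggered by platelets, treats if P < 1.25 x N. Both apply when P is below the smaller of the two limits. These are equal at N = 15,000/1.25 = 12,000.

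| Platelet nadir N | 1.25 x N | When the rules conflict (platelets trigger B.3) |
|---|---|---|
| 10,000 | 12,500 | Always; e.g. P = 12,000 is a 20% rise |
| 12,000 | 15,000 | Always |
| 13,000 | 16,250 | Only if P < 15,000 |
| 15,000 or more | 18,750 or more | Never, since P cannot be below the nadir |

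If WBC triggers B.3 instead, the rules conflict whenever P < 15,000.

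**Which nadirs qualify.** In B.1 (baseline platelets at least 75,000, with WBC and ANC also adequate), any nadir below 15,000 lies in the lowest row, below 25,000. In B.2 a fall of at least 50% is needed. A nadir of 12,000 therefore qualifies from a baseline of 2 x 12,000 = 24,000 upward, and every nadir below 15,000 qualifies from a baseline of 30,000 upward. A child with baseline platelets below 30,000 and falls under 50% in both platelets and WBC is outside B.3.

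**Dose at stake.** A full course is 40 x 4 = 160 mg/m2. Section 6.2.2 gives 0. B.3 gives half of what was scheduled:

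| Scheduled dose | B.3 course dose, mg/m2 |
|---|---|
| 100% | 160 x 0.5 = 80 |
| 75% | 0.75 x 160 x 0.5 = 60 |
| 67% | 0.67 x 160 x 0.5 = 53.6 |
| 50% | 0.50 x 160 x 0.5 = 40 |
| 33% | 0.33 x 160 x 0.5 = 26.4 |

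**Which cycles.** Cycle 2 starts 2 to 8 weeks after the taper ends (5.7.6). Suppose Cycle 1 is given at the start of the taper. With the suggested 2- to 4-week fast taper (5.6.2), Cycle 2 may start between 2 + 2 = 4 and 4 + 8 = 12 weeks later, and day 42 (6 weeks) can fall in that window. With the suggested 10-week standard taper (5.6.1), Cycle 2 cannot start before 10 + 2 = 12 weeks, so B.3 cannot direct dosing at day 42. Cycles 3 to 7 follow the 6-week schedule directly.

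**Clinical position at day 42.** Section 9.2.1 puts marrow recovery at days 28 to 31, so day 42 is 11 to 14 days later. If platelets have been below 20,000 since day 13 or earlier (42 - 13 = 29 days, more than 4 weeks), the child also meets the Grade 4 definition in 11.19. A hold fits the schedule: the window runs to day 42 + 14 = 56.

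**The case against.** The best defense is that the roles are already divided. Section 5.7.6 sends delays to section 6, 5.7.1 sends dose size to Appendix 5, and the two use different inputs (current counts versus nadirs). That is the sensible reading, and many clinicians would hold. But it is not stated, and B.3 does more than set a dose: it fixes the recheck interval and then directs treatment at day 42.

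Other objections stand as limits:
- **Frequency.** Section 9.2 puts the risk of Grade III hematologic toxicity at this dose below 10%, and 1.7 reports two Grade 3 thrombocytopenias in a 45-patient post-transplant study. Neither measures this exact case, but both suggest that it is uncommon.
- **Transfusion.** Section 6.2.2 itself mentions transfused children. Transfusion can lift a count past either limit without marrow recovery, so the boundaries above describe recorded counts only.
- **Scope of B.3.** It refers to a single table directly after B.2, so it may cover only low-baseline children. That narrows the overlap without removing it.
- **Recovery days.** The list in 9.2.1 includes higher-dose use, so the 11 to 14 days are indicative.
- **Status.** Section 6.2 and its pointer to Appendix 5 describe the adjustments as guidelines, and 5.7 allows azacitidine to be held.

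A reader might infer that the neutrophil hold conflicts with B.3 in the same way. The text does not support that: B.3 looks at WBC and platelets, so ANC below 500 alone does not trigger it. The B.1 row giving 50% for an ANC nadir below 0.5 sets the next dose from the nadir, which is compatible with a hold on the pre-cycle count.

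**Conclusion.** The contradiction is in the current text. A child with a table-qualifying nadir, platelets below 15,000/uL and no 25% rise in WBC or platelets by day 42 is held under 6.2.2 and treated at 50% under B.3, with no stated precedence. It is clearest in Cycles 3 to 7 and reaches Cycle 2 only when day 42 falls within its post-taper window. This rests on reading 6.2.2 as applying before every cycle, which 6.2 states, and on B.3 as written, without an implied floor.

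A reader might go further and infer that every cycle from 2 to 7 is affected; the tie between Cycle 2 and the taper rules that out. A reader might also infer that the relapse or toxicity estimates are distorted, since more than two dose reductions is a safety endpoint (8.3.5) and holds over 6 weeks are analyzed separately (5.7). The documents give no frequency for the case, and nothing in them shows a change in any trial estimate. This is a minor-to-moderate safety wording fix.

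**What to change.** Add the same statement to 6.2.2 and to Appendix 5 B:

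> The 6.2.2 hold limits (pre-cycle platelets <15,000/uL; ANC <500 not responsive to GCSF) override the Appendix 5 dose rules, including the day-42 50% rule. Appendix 5 sets the dose only once no hold criterion is met.

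This adds no visits, samples or procedures. The downside is small: some cycles will start later or be missed, and a hold beyond 6 weeks moves the child into the separate analysis that 5.7 already provides for.
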